12.2. Concomitant Medication (if applicable)

Throughout the study Investigators might prescribe any concomitant medications or treatments deemed necessary to provide adequate supportive care except for those listed in the exclusion criteria. If these were required, the participant will be withdrawn.

Any medication, other than the study medication had taken during the study will be recorded in the CRF.

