Statistical analysis	
- Descriptive analysis: All statistical tests used a significance level of P=0.05, two tailed tests are performed for all analyses used statistical testing. Descriptive analysis for quantitative data will include count, mean with 95% CI, standard deviation, median, minimum and maximum. For qualitative categorical variables; frequency and percentage and 95% confidence interval will be applied.

Stopping rules	
DVT PE Major bleeding Allergy APTT value increases by 2-2.5 folds According to investigator evaluation

Table of Contents

Title Page	1
1. Synopsis	2
Table of Contents	6
2. LIST OF ABBREVIATIONS	9
3. SIGNATURE(S) PAGE	10
4. INTRODUCTION	11
4.1. Background	11
4.2. Correlative studies:	11
4.3. Study Rationale	12
5. STUDY OBJECTIVES	12
5.1. Primary Objectives	12
5.2. Secondary objectives	12
6. TRIAL DESIGN	12
6.1. The pre-operative Phase	12
6.2. The operative Phase	13
6.3. The Follow-up Phase	13
7. FLOW CHARTS:	13
7.1. STUDY FLOW CHARTS:	13
7.2. STUDY PHASES	14
8. STUDY OUTCOME MEASURES	15
8.1. Primary Endpoints	15
8.2. Secondary Endpoints	16
9. STUDY POPULATION	16
9.1. Recruitment strategy:	16
9.2. Inclusion Criteria	16
9.3. Exclusion Criteria	16
10. STUDY PROCEDURE:	17
10.1. Selection of the study population:	17
10.2. Case Report Form	17
11. SOURCE DATA	17

12.	TREATMENT OF TRIAL PARTICIPANTS	18
12.1.	Description of Study Medication(s)	18
12.2.	Concomitant Medication (if applicable).....	19
13.	DATA COLLECTION	19
15.1.	DATA MANAGEMENT	20
15.2.	AMENDMENT TO THE PROTOCOL.....	20
15.2.1.	Protocol Deviations	20
15.2.2.	Onsite Audits.....	20
15.2.3.	Study Monitoring	21
15.3.	PREMATURE DISCONTINUATION OF STUDY.....	22
16.	SAFETY REPORTING AND DEFINITIONS	22
16.1.	Adverse Events Monitoring.....	22
16.2.	Reporting Period.....	23
16.3.	Adverse Event (AE):	23
16.4.	Serious Adverse Events	24
16.4.1.	Instructions for Reporting Serious Adverse Events	24
17.	STATISTICAL METHODOLOGY	24
17.1.	Determination of Sample Size.....	24
17.2.	Analysis Variables:.....	25
17.2.1.	Primary analysis variables:.....	25
17.2.2.	Secondary analysis variables:.....	25
17.2.3.	Statistical Method:.....	25
17.2.4.	Interim Analysis	25
18.	ETHICS.....	25
18.1.	INDEPENDENT ETHICS COMMITTEE (IEC) OR INSTITIUTIONAL REVIEW BOARD (IRB).....	25
18.2.	Ethical principles:	26
18.3.	Laws and regulations:	26
18.4.	PATIENT INFORMATION AND CONSENT	26
18.5.	DISCONTINUATION OF THE STUDY	27
18.5.1.	PREMATURE DISCONTINUATION OF STUDY	27

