- 2- Multicenter Trial of Desirudin for the Prophylaxis of Thrombosis: An Alternative to Heparin-Based Anticoagulation (DESIR-ABLE) shows that no patients experienced primary endpoints which is major bleeding and no new onset of symptomatic thrombosis requiring medical or surgical intervention or death.⁷

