6.2. The operative Phase

During this phase, patient's registries for the type of surgery done, Type of anesthesia, patient position and type of prosthesis, & blood transfusion during surgery should be recorded. And IMP dispensing 6 hours after surgery or upon adequate hemostasis will be done. APTT will be done 4 & 8 hours after the first dose

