8. STUDY OUTCOME MEASURES

8.1. Primary Endpoints

Primary end points included new onset symptomatic thrombosis requiring medical or surgical intervention or death due to thrombosis defined as fatal PE, ischemic

Sponsor: Minapharm Pharmaceuticals
Protocol Number: Sub-Thromb-001
Version: 1 amendment 1

stroke, mesenteric thrombosis, or myocardial infarction.

The number of clinical PE events will be measured by spiral CT

Mean changes in APTT where it will be done before first dose, 4 & 8 hours after first dose then on days 1,8,15 post operatively

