9.2. Inclusion Criteria

Patients aged 18 years of age or older

- Body Weight >60 kg
- Patients undergoing major orthopedic operations Total knee & hip Arthroplasty
- Patients ready to sign (ICF)

Patients should discontinue any agents that affect haemostasis prior to the study medication use unless strictly indicated. These agents include medications such as: anticoagulants, thrombolytics, non-steroidal anti-inflammatory agents (including Ketorolac tromethamine), preparations containing aspirin, systemic salicylates, ticlopidine, dextran 40, clopidogrel, other anti platelet agents including glycoprotein IIb/IIIa antagonists or systemic glucocorticoids.

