9.3. Exclusion Criteria

Significant bleeding injury such as solid organ laceration or intracranial bleed at discretion of attending physician

Hypersensitivity to Hirudin or prior documented allergy to its components

Pregnant or breast feeding females

Hemorrhagic stroke in preceding 3 months

Abnormal baseline coagulation characterized by an INR >1.4 , obtained at the discretion of the treating clinician

Required therapeutic anticoagulation for atrial fibrillation, prior VTE, or mechanical heart valve
Treatment with concomitant anti-platelet agent other than aspirin 326 mg or more daily
Subjects with a life expectancy less than 1 month

10. STUDY PROCEDURE:

10.1. Selection of the study population:

Subjects will be selected according to inclusion and exclusion criteria, willing to sign informed consent and able to complete the study.

Subject's informed consent had to be obtained and documented in accordance with local regulations, ICH-GCP requirements, and the ethical principles that have their origin in the principles of the Declaration of Helsinki.

Prior to obtaining informed consent, information should had been given in a language and at a level of complexity understandable to the subject in both oral and written form by the investigator or designee. Each subject should have the opportunity to discuss the trial and its alternatives with the investigator. the written Informed Consent Form should have been signed and personally dated by the subject, or his legal representative, and by the person who conducted the informed consent discussion (investigator or designee). The subject or his legal representative must had received a copy of the signed and dated Informed Consent Form. As part of the consent process, each subject must have consented to direct access to his medical records for trial-related monitoring, auditing, IRB/IEC review and regulatory inspection.

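### A participant who needs an exclusion-listed treatment is to be withdrawn, and nothing in the plan keeps that patient on the Day 8 and Day 15 assessments

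*Protocol*

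**What the plan says.** Protocol 12.2 lets investigators give any supportive treatment except those named in the exclusion criteria. If one of those is needed, "If these were required, the participant will be withdrawn". The treatments named in 9.3 are "Treatment with concomitant anti-platelet agent other than aspirin 326 mg or more daily" and "Required therapeutic anticoagulation for atrial fibrillation, prior VTE, or mechanical heart valve".

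The synopsis has a stopping-rules cell that reads only "DVT PE Major bleeding Allergy APTT value increases by 2-2.5 folds According to investigator evaluation". Section 15.3 repeats nearly the same triggers as grounds on which the sponsor may end the trial. Section 18.5.1 repeats some of them: the APTT rise, and adverse events that make termination necessary.

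The primary endpoint in 8.1 is "new onset symptomatic thrombosis requiring medical or surgical intervention or death due to thrombosis". Section 7.2 schedules thrombosis, PE and bleeding assessments on Days 1, 8 and 15. Protocol 17.2 and SAP 8.2 define the thrombosis and major-bleeding results as proportions of patients, but SAP Tables 8 and 11 lay them out visit by visit.

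Protocol Section 6 and SAP Section 2 describe the trial's patients as having full data and two weeks of follow-up. SAP Table 20 is titled for discontinuation of treatment, while its reason row refers to discontinuation from the study.

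**The concern.** Stopping a drug and ending observation are different decisions, and 12.2 does not separate them. If the site takes it to mean leaving the study, the Day 8 and Day 15 assessments lapse for that patient. The reasons for leaving (a new need for an anti-platelet agent or anticoagulant and, if sites apply the synopsis list to individuals, bleeding, thrombosis or a raised APTT) may be related to the outcomes being estimated, so the loss need not be random.

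Two things are at stake. One is later events: PE, thrombotic death or major bleeding after withdrawal would rest on SAE reporting instead of planned assessment. The other is the denominator. The design wording about full data and two weeks of follow-up, read literally, favours leaving withdrawn patients out, and the SAP names no analysis set that would settle it.

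**Working it through.** **Does any text keep the patient under observation?**
- 15.3 and 18.5.1 assure follow-up, but only if the whole trial is terminated or suspended.
- 16.1 follows adverse events to resolution only where they are causally related to the product. It records all other adverse events until the end of study for that patient, a date that withdrawal may bring forward.
- 16.2 runs SAE reporting to the end of the follow-up period. It does not require a Doppler, a PE assessment or a bleeding assessment on Day 8 or Day 15.

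None of these keeps one withdrawn patient on the schedule.

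**Who can reach the rule?** Section 9.2 says: "Patients should discontinue any agents that affect haemostasis prior to the study medication use unless strictly indicated". A patient who could stop clopidogrel before surgery but must restart it within 15 days falls under 12.2. If the synopsis list is applied to individuals, exit can come as early as Day 0, because "APTT will be done 4 & 8 hours after the first dose".

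**Inputs for size.** Planned N = 100. DVT rates in the protocol:
- 6/174 = 3.4% (proximal) and 13/174 = 7.5% (overall), from 4.2;
- 12.5%, from 17.1. The plan's own precision figure reproduces: 1.96² × 0.125 × 0.875 / 0.05² = 168.06, against 168 stated. The gap between 168 and 100 is a separate matter.

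These are DVT rates and are not stated to be symptomatic, so they probably overstate the rate of the primary endpoint. The other study cited in 4.2 reported "no new onset of symptomatic thrombosis requiring medical or surgical intervention or death", a rate of 0.

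**Expected later DVTs in patients withdrawn for reasons other than thrombosis.** Assume k = 1 to 5 of 100. Expected number = k × rate, using the full 15-day rate and so erring high:

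| k | 0% | 3.4% | 7.5% | 12.5% |
|---|---|---|---|---|
| 1 | 0 | 0.03 | 0.07 | 0.13 |
| 3 | 0 | 0.10 | 0.22 | 0.38 |
| 5 | 0 | 0.17 | 0.37 | 0.63 |

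This takes withdrawn patients to have the same risk as the rest. At twice the highest rate, k = 5 gives 5 × 0.25 = 1.25.

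**Effect of one missed event** (exact Clopper-Pearson 95% intervals):
- Primary: 8/100 = 8% (3.52-15.16%) becomes 7/100 = 7% (2.86-13.89%).
- Major bleeding: 1/100 = 1% (0.03-5.45%) becomes 0/100 (upper limit 3.62%).

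**Effect of the denominator alone.** Leaving out five event-free patients turns 8/100 into 8/95 = 8.4%. Leaving out one patient together with a counted event gives 7/99 = 7.1%. The direction depends on who is dropped.

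**The case against.** The best reply is that the sentence reaches few patients and costs little.

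- **Reach.** Section 9.3 names anticoagulation for atrial fibrillation, prior VTE or a mechanical valve, not for a DVT or PE arising on study. A reader might infer that 12.2 removes the primary-endpoint cases themselves. The wording does not support that, and the event that prompts treatment would normally be recorded already. This part of the reply stands.
- **Meaning.** A reader might also take it as settled that the patient leaves the study. The text supports either reading: 12.2 sits under treatment of participants, and Table 20 mixes the two ideas. The gap is the ambiguity.
- **Stopping rules.** It would be too strong to say that the plan never says what stops. Section 15.3 attaches the triggers to the trial. What is missing is a rule for the patient.
- **Denominator.** A reader might infer a planned completer analysis. At the extreme, 8/100 would become 0/92 (upper limit 3.9%) if all eight thrombosis patients were withdrawn and dropped. The design sentence is not an analysis set, and SAP Table 20 is headed N = 100, so the documents do not direct this. They do not rule it out either.
- **Safety net.** A thrombosis needing intervention, or a major bleed, would ordinarily meet the seriousness criteria in 16.4 and be reported under 16.2. This stands and limits the harm, although SAE reporting does not replace a scheduled assessment.
- **APTT.** Keeping patients on every assessment would put off-drug values into Table 10. This is a fair objection, and the fix has to deal with it.

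**Conclusion.** The point holds as a minor one. Section 12.2 withdraws the participant without separating drug from study, no patient-level rule exists for the synopsis triggers, and no text keeps such a patient on the Day 8 and Day 15 assessments.

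The likely effect on the primary proportion is between nothing and about one event, that is, about one percentage point at N = 100. This rests on an assumed 1 to 5 withdrawals for reasons other than thrombosis, on the protocol's own DVT rates standing in for symptomatic events, and on withdrawn patients having risk similar to the rest. A larger effect would need withdrawn patients to be dropped together with their counted events, which the plan does not instruct.

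**What to change.** - **Section 12.2:** state that the patient stops study drug only, and that the Day 8 and Day 15 thrombosis, PE, bleeding and adverse-event assessments continue unless consent is withdrawn.
- **Beside 15.3 and 18.5.1:** add the same patient-level rule for DVT, PE, major bleeding, allergy and APTT rise, leaving the sponsor's right to end the trial as it is. Point the synopsis cell to it.
- **SAP 8.2, Tables 8 and 11:** report the thrombosis and major-bleeding proportions cumulatively over Days 1 to 15 in all treated patients, counting the event that led to stopping. Show bleeding after rescue anticoagulation within the total and also separately.
- **SAP Table 10:** summarise APTT for on-drug values only and list off-drug values separately.

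The cost is a few sentences and table lines, since the visits are already scheduled. The downside for the sponsor is that reported event and bleeding rates may be slightly less favourable.

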13. DATA COLLECTION

The Investigator is required to prepare and maintain adequate and accurate case histories designed to record all observations and other data reliable to the study for each study participant.

Subjects who are screened but choose not to continue in the study or those that are found to be ineligible for the study will be considered “screen failures”. The reason for the failure will be recorded on the source document and in the CRF.

The Clinical Research Associate (CRA) will verify the paper CRF documentation for each subject against the source documents at the study center. Instances of missing or uninterpretable data will be brought to the attention for resolution. A copy of the source document and CRF will be placed in the Investigator’s study file and the original CRF will be kept by Minapharm at the end of the study. The CRF will be the sole property of the Minapharm.

Data reported in the paper CRF derived from source documents should be consistent with source documents or the discrepancy should be explained. Only the investigator/designee and clinical research coordinator are authorized to make entries on the paper CRF.

The investigators will be responsible to ensure the accuracy, completeness and timelines of the data reported.

All source documents and reports must be reviewed by the designated clinical team and data entry staff, who will ensure that they are accurate and complete. Clinical assessments data must be entered into source data. Adverse events must be graded, assessed for severity and causality, and reviewed by the site investigator or designee.

Data collection is the responsibility of the clinical trial staff at the site under the supervision of the site investigator. During the study, the investigator must maintain complete and accurate documentation for the study. All relevant clinical data from source documents will be entered into the paper CRF.

After completion of the paper CRFs by the investigator, monitor will review all subject paper CRFs for completeness and accuracy. Requests for clarifications or correction will be sent to the investigator, if necessary. Statistical analysis will be carried out after all necessary corrections have been done and database has been locked.

Minapharm will serve as the statistical and data management for this study and will be responsible for data management, quality review, analysis, and reporting of the study data.

The protocol and paper CRF are confidential documents. The paper CRFs will be supplied by the Minapharm. Appropriate information for the completion of paper CRF will be provided to all participating centers. The paper CRFs must accurately reflect data contained in subject's records (i.e. source documents). In order to maintain confidentiality, the subject will be identified only by his/her assigned study subject number and/or initials.

Clinical data will be entered into paper CRF from the source documents. The data system includes password protection and internal quality checks to identify data that appear inconsistent, incomplete, or inaccurate.

Queries generated during data entry will be sent to investigator for resolution and record of the same would be kept.

15.1. DATA MANAGEMENT

All data collected in this study will be entered manually by data entry team on Oracle database specially designed to meet the needs of clinical trials prepared by Minapharm.

Edit checks will be run on the data and queries issued as needed and queries will be resolved. Full quality control data verification will be done and then data will be declared clean. Database will be locked after Minapharm medical department approval.

Extraction of data for statistical analysis will be done once database lock occurs. All data collected in the paper CRFs will be documented in subject data listings and summarized in tables, as appropriate.

15.2. AMENDMENT TO THE PROTOCOL

Modifications of the signed protocol are only possible by approved protocol amendments authorized by Minapharm. The protocol amendments will be approved by the IRB/IEC prior to implementation. The Investigator must not implement any deviation from, or change to the protocol, except where it is necessary to eliminate an immediate hazard to trial subject or when the change(s) involves only logistical or administrative aspects of the trial.

15.2.1. Protocol Deviations

The Investigator will not deviate from the protocol without prior written approval from sponsor (or designee), except in medical emergencies. In such cases, Minapharm must be notified as soon as possible. The governing IEC will be informed of all protocol deviations by the Investigator.

15.2.2. On-site Audits

Minapharm may conduct audits at the study center(s). Audits will include, but will not be limited to, study medication supply, presence of required documents, the informed consent process, and comparison of paper CRFs with source documents. The investigator agrees to participate with audits conducted at a reasonable time in a reasonable manner. These audits are for the purpose of verifying the adherence to the protocol, the completeness and exactness of the data being entered

in the CRF, and compliance with regulations. Subject confidentiality will be maintained during all audits. Regulatory authorities may also audit the investigator during or after the study. The investigator must contact Minapharm immediately if this occurs and must fully cooperate with the audits conducted at a reasonable time in a reasonable manner.

15.2.3. Study Monitoring

The clinical research associate (CRA) will undertake the study monitoring/supervision. In accordance with applicable regulations, ICH-GCP, Minapharm monitors will contact the site prior to the subject enrollment to review the protocol and data collection procedures with site staff. In addition, the monitor will periodically contact the center, including conducting on-center monitoring visits at an appropriate frequency, according to the monitoring plan.

During these contacts, the monitor will:

1. Check the progress of the study.
2. Review study data collected.
3. Conduct source document verification and CRF data entry.
4. Identify any issues and address their resolution.

This will be done in order to verify that the:

1. Data are authentic, accurate, and complete.
2. Safety and rights of subjects are being protected.
3. Study is conducted in accordance with the currently approved protocol (and any amendments), ICH-GCP, and all applicable regulatory requirements.

The investigator agrees to allow the monitor direct access to all relevant documents and to allocate his/her time and the time of his/her staff to the monitor to discuss findings and any relevant issues.

Monitoring visits at each investigative site will be conducted by the CRAs at regular intervals. The first monitoring visit will be conducted immediately after the enrollment of first subject in the study and the subsequent monitoring visits will be conducted based on the recruitment status and activities at the site. The CRAs are responsible for applying the applicable monitoring plan. Any data clarification from Data Management (DM) will be resolved by the site. In addition, the CRAs will be in frequent contact through verbal and written communication with the investigators. It is essential that the CRAs have access to all documents (related to the study and the individual participants) at any time when these are requested. In return, the CRA will adhere to all requirements for subject confidentiality as outlined in the ICF. The investigator and his/her staff will be expected to cooperate with CRA, to be available during a portion of the monitoring visit to answer questions, and to provide any missing information.

Original subject records (source documents) will be audited or reviewed during the course of monitoring to verify the accuracy of the source documents and accuracy of data entered from these source documents into the paper CRF.

Source data is defined as all information in original records and certified copies of original records of clinical findings, observations, or other activities in a clinical trial necessary for the reconstruction and evaluation of the trial. Source documents are original documents, data, records and subject files.

15.3. PREMATURE DISCONTINUATION OF STUDY

The sponsor may prematurely terminate the trial if any of the following situations occurs:

APTT value of the subject increased by 2-2.5 folds.

Comprehensive deficiency in the recorded data or protocol compliance so that the results of the study cannot be reliably assessed.

Occurrence of AEs necessitating termination such as major bleeding, DVT, PE, allergy or for any other reason according to investigator evaluation.

The IRB/IEC changes its opinion regarding the safety/efficacy/relevance of the compound.

Regulatory authority decision.

If the trial is prematurely terminated or suspended for any reason, the investigators and subsequently the trial subjects will be informed promptly, standard therapy and follow-up for subjects will be assured and, where required by the applicable regulatory requirement(s), the relevant regulatory authority(s) will be informed. The IRB/IEC and all trials sites will be informed promptly and provided with a detailed written explanation for the termination or suspension. As directed by Minapharm, all study materials must be collected and all CRFs completed to the greatest extent possible.

